9.5.5.5. Schedule

Table 2 below summarizes procedures and evaluations to perform at each visit.

| | |
|--|--------------|
| 2022.08.11_RGnCON_Prot_Final_V2.0_clean_public | Page 45 / 82 |
|--|--------------|

| | | |
|--------|---|---|
| RGnCON | Clinical Investigation Plan Version 2.0 - 11 August 2022 |  |
|--------|---|---|

Table 2: Schedule of procedures and evaluations

| | D0 | | D7 | | D14 (remote) | D52 |
|--|------------------|-----------------|------------------|-----------------|-----------------|-----|
| | Before treatment | After treatment | Before treatment | After treatment | | |
| Patient information / Informed consent | X | | | | | |
| Eligibility criteria | X | | | | | |
| Pregnancy test for women of childbearing potential | X | | | | | |
| Randomization | X | | | | | |
| Demographic and clinical data | X | | | | | |
| NPC | X | X | X | X | | X |
| Cover test | X | X | X | X | | X |
| Maddox rod test | X | X | X | X | | X |
| Stabilometric test | X | X | X | X | | X |
| TMT A&B | X | | | X | | |
| SCAT5 symptom evaluation tool | X | | X | | X | X |
| Blood sampling | X | | | | | X |
| 20-min treatment session | X | | X | | | |
| Collection of AEs and DDs that previously occurred | | X | X | X | | X |

9.5.6. Monitoring

Monitoring activities will be performed by [REDACTED]

During the investigation, [REDACTED] monitors will perform:

- **Source data verification during on-site monitoring visits** to confirm that data entered into the eCRF by authorized site personnel are complete, accurate, and verifiable based on source documents. During these visits, the monitors will also check that the informed consent process was performed as planned in section 9.12.
- **Source data review during remote monitoring** (through telephone and/or email) to confirm that data entered into the eCRF by authorized site personnel are complete and consistent. These remote monitoring will also allow to check the inclusion progress, data entry progress and collect any missing documents from the site.

The monitors will ensure that the investigation is conducted according to this Clinical Investigation Plan (CIP), the Good Clinical Practice (GCP) and applicable laws and regulations.

Monitoring will be performed according to the process defined in the Clinical Monitoring Plan, which will notably describe the extent and frequency of monitoring.

Source documents are paper or electronic documents in which patient data are recorded and documented for the first time. They include, but are not limited to, hospital records, clinical and office charts, laboratory notes, memoranda, evaluation checklists, pharmacy dispensing records, recorded data from automated instruments, copies of transcriptions that are certified after verification as being accurate and complete, microfiche, photographic negatives, microfilm or magnetic media, X rays, patient files, and records kept at pharmacies, laboratories, and medico technical departments involved in a clinical investigation. Source documents will be saved after the end of the investigation during 15 years by the investigators or site.

The investigators and site must provide authorized personnel (monitors, sponsor, regulatory authorities, Ethics Committee) direct access to applicable source documents for investigation-related monitoring, sponsor audits, health authorities inspections and Ethics Committee review.

| | | |
|--------|---|---|
| RGnCON | Clinical Investigation Plan Version 2.0 - 11 August 2022 |  |
|--------|---|---|

9.6. Statistical Considerations

9.6.1. Sample Size Justification

For a sample size of 50 patients, the probability of observing at least one ADE will be 0.87 considering a probability of ADE of 0.04. The sample size calculation was performed with SAS® v9.4.

9.6.2. Analysis Population

All analyses will be performed in the **Full Analysis Set (FAS)**, which will comprise all included patients who have been treated at least once with RGn550 device. Patients will be assigned to the treatment group as treated.

9.6.3. Statistical Analysis

Full details related to statistical analysis will be provided in the Statistical Analysis Plan.

The statistical analysis will be performed using SAS® Viya v9.4 (or a more recent version).

The global significance level (type I error rate) will be set at $\alpha = 0.05$ (two-sided). Adjustment for multiplicity is not applicable for the primary endpoint and no adjustment for multiplicity is planned for secondary endpoints.

Continuous data will be described by the number of missing data, number of data analyzed, mean, standard deviation, median, Q1, Q3, minimum, maximum.

Categorical data will be described by the number of missing data, frequencies and percentages of patients in each modality. The percentage of patients will be calculated once missing data are excluded from the denominator.

9.6.3.1. Primary Endpoint Analysis

The proportion of subjects with at least one ADE will be calculated along with the 95% exact Clopper-Pearson confidence interval in the FAS, by treatment groups and overall.

Of note, a lost to follow-up rate of 10% is anticipated. If this rate is higher, an analysis of the primary endpoint using percentage of patient-years will be considered in the Statistical Analysis Plan.

9.6.3.2. Secondary Endpoints Analysis

ADEs per severity

A descriptive analysis with 95% exact Clopper-Pearson confidence interval of mild, moderate and severe ADEs will be provided in the FAS, by treatment groups and overall.

AEs

All AEs will be described in the FAS, for each System Organ Class (SOC) and Preferred Term (PT) class using MedDRA (Medical Dictionary for Regulatory Activities) terminology, by treatment groups and overall.

DDs

All DDs will be described in the FAS, by treatment groups and overall.

| | |
|--|--------------|
| 2022.08.11_RGnCON_Prot_Final_V2.0_clean_public | Page 48 / 82 |
|--|--------------|

Secondary performance analyses

The secondary performance analyses will be performed in the FAS by treatment groups, excluding data that would be collected after the following intercurrent event: treatment group switch during follow-up.

Imputation of missing data will be handled by the mixed model (details will be provided in the Statistical Analysis Plan).

The analyses will be performed as follows:

- For the evolution of the below parameters, the following timepoints will be compared: (D0 after treatment - D0 before treatment, D7 before treatment - D0 before treatment, D7 after treatment - D0 before treatment, and D52 – D0 before treatment) and a mixed effect regression model will be used with a patient random effect. Group effects (5 Hz vs 10Hz), period effects (D0 before, D0 after, D7 before, D7 after and D52) and the group-by-period interaction will be added as fixed effects. The stratification variables will be added in the model as covariates.
 - Automated oculomotor and oculopostural functions:
 - Convergence, evaluated with the Near Point of Convergence (NPC) (>5 cm vs ≤5 cm)
 - Deviation as evaluated with the cover test (normal fixation or light restitution movement or important restitution movement or deviated eye without restitution movement)
 - Horizontal deviation as evaluated with the Maddox rod test (orthophoria or exophoria or esophoria and measure in diopter)
 - Vertical deviation of the right eye as evaluated with the Maddox rod test (orthophoria or hypophoria or hyperphoria and measure in diopter)
 - Vertical deviation of the left eye as evaluated with the Maddox rod test (orthophoria or hypophoria or hyperphoria and measure in diopter)
 - Balance function:
 - Statokinesigram area (m²)
 - Difference between left distribution and right distribution (%)
- For the evolution of executive function, the following timepoints will be compared: (D0 before treatment – D7 after treatment) and a mixed effect regression model will be used with a patient random effect. Group effects (5 Hz vs 10Hz), period effects and group-by-period interaction will be added as fixed effects. The stratification variables will be added in the model as covariates.
 - TMT A: time (s)
 - TMT A: number of errors
 - TMT B: time (s)
 - TMT B: number of errors
 - TMT B-A: time (s)
 - TMT B-A: number of errors
- For concussion syndrome symptoms (SCAT5): For the analysis at D0 before treatment, D7 before treatment, D14 and D52, a mixed linear regression model will be used with a patient random effect. Group effects (5 Hz vs 10Hz), period effects and group-by-period interaction will be added as fixed effects. The stratification variables will be added in the model as covariates. This model will be run for:
 - The total number of symptoms (score from 0 to 22)
 - The symptom severity (score from 0 to 132)

| | | |
|--------|---|---|
| RGnCON | Clinical Investigation Plan Version 2.0 - 11 August 2022 |  |
|--------|---|---|

- A description analyses of blood markers at each time point and the change from baseline to each time point will be assessed by groups and overall.

Sensitivity analysis:

A sensitivity analysis will be conducted on the secondary performance endpoints in the FAS without excluding any data that would be collected after intercurrent events.

Of note, data of patients with a second concussion that occurred after RGn550 first treatment session will be considered before the onset of the concussion. Similarly, data of patients with a contraindication to RGn550 that occurred after RGn550 first treatment session will be considered before the onset of the contraindication.

This sensitivity analysis will be performed only if the proportion of excluded patients exceeds 10% (at least 5 patients excluded).

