9.5.4.2. Secondary Endpoints

The secondary endpoints are:

- The **incidence of RGn550's ADEs per severity** throughout the investigation:
 - Incidence of mild ADEs
 - Incidence of moderate ADEs
 - Incidence of severe ADEs
- The **incidence of RGn550's AEs** throughout the investigation
- The **incidence of RGn550's DDs** throughout the investigation.
- The evolution, before and after treatment session at D0 and D7 and then at D52, of:
 - **Automated oculomotor and oculopostural functions**, as assessed through:
 - Convergence, evaluated with the measure of the Near Point of Convergence (NPC)
 - Deviations, evaluated with the cover test and Maddox rod test
 - **Balance function**, as assessed through the following static stabilometric parameters:
 - Statokinesigram area
 - Left/right distribution
- The evolution, before treatment session at D0 and after treatment session at D7 of **executive function**, as assessed with the TMT A&B
- The evolution of **concussion syndrome symptoms** as assessed by the patient with the SCAT5 symptom evaluation tool at D0 before treatment, D7 before treatment, D14 and D52
- The evolution from D0 before treatment to D52 of the concentration of the following **blood markers**:
 - Anti-inflammatory cytokines InterLeukin (IL)-1 receptor antagonist, IL-4, IL-6, IL-10, IL-11 and IL-13
 - S100 calcium binding protein B (S100B)
 - Glial Fibrillary Acidic Protein (GFAP)
 - Ubiquitin C-terminal Hydrolase-L1 (UCH-L1).

These secondary endpoints have been chosen since:

- Convergence insufficiency is an emerging oculomotor-related outcome after a sport-related concussion [26] and the NPC is one of the primary diagnostic tests used to assess convergence insufficiency. Of note, convergence insufficiency rate following concussion was reported to range from 42% to 55% [7].
- The cover and Maddox rod tests are recognized tests to assess ocular deviations [27, 28]. In particular, the Maddox rod test has been used for more than a century in ophthalmology [28].
- Stabilometry is an objective and reproducible method for the recording and evaluation of balance function, in particular following neurologic impairment [29]. Of note, the statokinesigram area is chosen as it is a parameter that might evolve with concussion evolution [30] while the left/right distribution is added as an exploratory parameter.

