Figure 8: Horizontal orientation of the Maddox rod to identify horizontal deviation (BI: Base In, BO: Base Out) [38]

[figure not shown]

Figure 9: Vertical orientation of the Maddox rod to identify vertical deviation (BD: Base Down, BU: Base Up, LH: Left Hyperphoria, Rh: Right hypophoria, RH: Right Hyperphoria) [38]

- **Static stabilometric test**

Static stabilometric parameters are measured with the use of a stabilometric platform equipped with sensors that monitor the evolution in time of the patient's center of pressure and its movements relative to the center of the platform. The signal is digitalized, evaluated by special computer program and results are visualized on the monitor and recorded [29].

The patient will be asked to stand on KFORCE Plates (a stabilometric platform manufactured by KINVENT HELLAS, see Figure 10) either barefoot or with his/her shoes and orthopedic inserts in case the patient has inserts. A 30 s-record will be performed, two times consecutively: one time with the patient's eyes open and one time with the patients' eyes closed.

Following these two records, the two values of the following parameters will be collected, and their mean will be calculated:

- The statokinesigram area

The statokinesigram is the projection onto a 2-dimensional space of the trajectory of the patient's center of pressure [39]. Its area is measured in mm². The larger the area is, the higher the patient's imbalance is.

- The left/right distribution

The left/right distribution comprises two percentages representing the patient's body weight distribution on his/her left versus right foot. If 50% is obtained for each foot, the patient is stable.

Figure 10: Picture of KFORCE Plates

- **TMT A&B**

The TMT is an executive function test reflecting various cognitive processes such as selective attention, motor activity and flexibility. In Part A, the subject is instructed to trace a line that connects circled numbers in consecutive order (see Appendix 12.2.1). In Part B, the subject is asked to trace a line that connects circled numbers and circled letters in consecutive order while alternating between numbers and letters (see Appendix 12.2.2). The time to perform the task, number of correct moves and number of errors are collected [31].

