#### 6.2.2. Secondary performance endpoints

According to section 9.5.4.2 of the Protocol, the following endpoints will be used to address Secondary performance objectives:

- Automated oculomotor and oculopostural functions will be used as recorded in the eCRF, before and after treatment session at D0 and D7 and then at D52:
  - Convergence, evaluated with the measure of the Near Point of Convergence (NPC)
  - Deviations:
    - Cover test
      - Normal fixation of both eyes
      - Abnormal with at least one eye
    - Maddox rod test:
      - Horizontal deviation (yes/no)
      - Vertical deviation right eye (yes/no)
      - Vertical deviation left eye (yes/no)
- Balance function will be used as recorded in the eCRF, before and after treatment session at D0 and D7 and then at D52:
  - Patient's eyes opened

- Statokinesigram area (mm^2)
- Left distribution (%)
- Right distribution (%)
- Patient's eyes closed
  - Statokinesigram area (mm^2)
  - Left distribution (%)
  - Right distribution (%)
- Rombert quotient (RQ)

The Romberg quotient is the ratio between the statokinesigram area (mm^2) with closed eyes (CE) and the statokinesigram area (mm^2) with opened eyes (OE), it will be calculated as follow :

$$RQ = CE/OE.$$

- Statokinetic distribution index (SKDI)

The stato-kinetic distribution index (SKDI) is the result of the STKG area multiply by the ratio of support distribution it will be calculated as follow:

$$SKDI (\text{mm}^2) = STKG \text{ area } (\text{mm}^2) \times (D/d^*)$$

\*D : Highest distribution value (%)

d : Lowest distribution value (%)

- TMT A&B before treatment session at D0 and after treatment session at D7:
  - TMT – A
    - Time to perform the task will be derived as:  
$$\text{Time to perform the task (in second)} = \text{minutes} * 60 + \text{second.}$$
    - Number of errors (will be used as recorded in the eCRF)
  - TMT –B
    - Time to perform the task will be derived as:  
$$\text{Time to perform the task (in second)} = \text{minutes} * 60 + \text{second.}$$
    - Number of errors (will be used as recorded in the eCRF)
  - TMT – B - A
    - Time to perform the task will be derived as:  
$$\text{Time to perform the task (in second)} = \text{Time to perform the task B} - \text{Time to perform the task A}$$
    - Number of errors will be derived as:  
$$\text{Number of errors} = \text{Number of errors B} - \text{Number of errors A}$$

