#### 8.5.1.1. Automated oculomotor and oculopostural functions and balance function

For the evolution of parameters of oculomotor and oculopostural functions and balance function defined in Section 0, the following timepoints will be compared: (D0 after treatment - D0 before treatment, D7 before treatment - D0 before treatment, D7 after treatment - D0 before treatment, and D52 – D0 before treatment). A mixed effect regression model (logistic model for a categorical parameters and a linear model for continuous parameters) will be used with a patient random effect. Group effects (5 Hz vs 10Hz), period effects (D0 before, D0 after, D7 before, D7 after and D52) and the group-by-period interaction will be added as fixed effects. The stratification variable gender (male/female) will be added in the model as covariates.

Note: the stratification variable concussion history within 6 months prior to inclusion (yes/no) will not be added in the model as too few patients had concussion history (cf. data review minutes of 18/07/2023).

The following template will be used for continuous parameters.

	Group of treatment		
Ref = D0 before treatment	RGn550 5Hz N=xx	RGn550 10Hz N=xx	Difference
Endpoint XXX at D0 after treatment			
Adjusted mean	x.xx	x.xx	x.xx
95% CI	x.xx ; x.xx	x.xx ; x.xx	x.xx ; x.xx
p-value	.	.	0.xxx
Endpoint XXX at D7 before treatment			
Adjusted mean	x.xx	x.xx	x.xx
95% CI	x.xx ; x.xx	x.xx ; x.xx	x.xx ; x.xx
p-value	.	.	0.xxx
Endpoint XXX at D7 after treatment			
Adjusted mean	x.xx	x.xx	x.xx
95% CI	x.xx ; x.xx	x.xx ; x.xx	x.xx ; x.xx
p-value	.	.	0.xxx
Endpoint XXX at D52			

		Group of treatment		
Ref = D0 before treatment		RGn550 5Hz N=xx	RGn550 10Hz N=xx	Difference
Adjusted mean		x.xx	x.xx	x.xx
95% CI		x.xx ; x.xx	x.xx ; x.xx	x.xx ; x.xx
p-value		.	.	0.xxx

From an mixed model including treatment (p=0.xxx), visit (p=0.xxx), treatment-by-visit interaction (p=0.xxxx) as fixed effects and variable xxx as random effect, variableyyy (p=0.xxx) as baseline covariate.

The following template will be used for categorical parameters.

	RGn550 10Hz vs RGn550 5Hz at visit 1	RGn550 10Hz vs RGn550 5Hz at visit 2	visit 2 vs visit 1 at RGn550 10Hz	visit 2 vs visit 1 at RGn550 5Hz
Endpoint XXX				
Odds ratio	X.X	X.X	X.X	X.X
95% CI	[X.X ; X.X]	[X.X ; X.X]	[X.X ; X.X]	[X.X ; X.X]

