## 10. CHANGES IN THE STATISTICAL METHODS FROM THOSE STATED IN THE PROTOCOL

This SAP is based on protocol version 2.0 and CRF version 2.0.

Changes in the statistical methods compared with those stated in the protocol are the following.

Add analysis subgroups:

- Subgroups analysis (“NPC > 5 at D0 before treatment”, “Horizontal deviation at D0 before treatment”, “Vertical deviation at D0 before treatment” (Maddox rod vertical – Left eye) and “Vertical deviation on at least one eye at D0 before treatment” (Maddox rod vertical – Both eyes), “number of previous concussions”).

Add secondary endpoints:

- Rombert quotient and Statokinetic distribution index calculation.

Add analysis of:

- NPC measurement in the subgroup “NPC > 5 at D0 before treatment”.
- Maddox rod horizontal score in the subgroup “Horizontal deviation at D0 before treatment”.
- Maddox rod vertical left eye in the subgroup “Vertical deviation at D0 before treatment”
- Maddox rod vertical both eyes in the subgroup “Vertical deviation at least one eye at D0 before treatment”.

Add descriptive analysis of ADE occurring during the first session (D0) and during the second session (at D7).

Add Exploratory analyses: study of potential relationship between drowsiness and concussion severity parameters.

There were no other changes in the statistical methods from those stated in the protocol.

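### Left/right weight distribution is modelled with its sign, so recovery towards 50/50 cancels between left- and right-leaning patients and a mean change does not show benefit

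*Protocol*

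**What the plan says.** Protocol 9.5.5.1 describes the measure as the percentage of body weight on each foot and sets the reference state: "If 50% is obtained for each foot, the patient is stable". It also plans to average the eyes-open and eyes-closed records: "the two values of the following parameters will be collected, and their mean will be calculated".

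Protocol 9.5.4.2 lists the measure under the secondary balance endpoints but gives it a lower status: the "left/right distribution is added as an exploratory parameter". Protocol 9.6.3.2 names the modelled variable as "Difference between left distribution and right distribution" in percent and does not say whether it is signed or absolute.

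SAP 6.2.2 uses the values as they stand in the eCRF. It lists "Left distribution" and "Right distribution" separately, once for eyes open and once for eyes closed. It adds a statokinetic distribution index (SKDI): sway area multiplied by the ratio of the higher to the lower percentage. SAP 8.5.1.1 then applies a mixed model ("logistic model for a categorical parameters and a linear model for continuous parameters"), with adjusted means, a between-arm difference and a p-value at each of four timepoints after baseline.

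SAP section 10 does not list the move from a difference to two separate percentages, and it closes with "There were no other changes in the statistical methods from those stated in the protocol".

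**The concern.** When the good state lies in the middle of the scale, improvement lowers left % in a patient who leans left and raises it in one who leans right. A model for the mean of left %, or of left minus right, adds these opposite movements together. It answers which side patients favour on average, not whether they stand more evenly.

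Two misreadings follow. A null result could be reported as no change in symmetry, or no difference between 5 Hz and 10 Hz, when symmetry did change. A non-null result carries no stated direction of benefit, because its sign depends on the mix of leaning sides. This matters because improved balance is one of the anticipated benefits in protocol 9.3.1, and protocol 9.2.3 says the two arms are compared to find the better frequency for safety and performance.

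**Working it through.** **Plan figure.** The documents give no SD, correlation or effect for this parameter, so there is no planned figure to reproduce. The only sample-size figure, 0.87 for at least one ADE, does reproduce (1 - 0.96^50 = 0.870) but has no bearing here.

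**Inputs from the documents.** Stable state 50/50 (protocol 9.5.5.1); left % and right % unfolded (SAP 6.2.2); linear mixed model (SAP 8.5.1.1); 50 patients randomised 1:1, so 25 per arm (protocol 9.6.1 and 9.5.5.1); two-sided alpha 0.05 (protocol 9.6.3).

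**Single patients.** Let L and R be the two percentages, with R = 100 - L, so L - R = 2L - 100.

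| Movement | Change in L - R | Change in absolute L - R |
|---|---|---|
| 60/40 to 50/50 | -20 | -20 |
| 40/60 to 50/50 | +20 | -20 |
| 60/40 to 40/60 | -40 | 0 |

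**Groups of 25, all fully recovering from a 20-point imbalance.**

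| Left / right leaners | Mean change in L - R | Mean absolute change |
|---|---|---|
| Even split | 0 | -20 |
| 15 / 10 | (15 x -20 + 10 x 20)/25 = -4 | -20 |
| 20 / 5 | (20 x -20 + 5 x 20)/25 = -12 | -20 |
| 25 / 0 | -20 | -20 |

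**Number of tests.** Two sides x two eye conditions x four timepoints = 16 between-arm p-values. Since R = 100 - L, each right % model mirrors its left % model, so 8 are duplicates.

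**SKDI.** The ratio is 1.5 at both 60/40 and 40/60, and 1.0 at 50/50, so it ignores direction. But area 400 at 60/40 gives 400 x 1.5 = 600, and area 600 at 50/50 gives 600 x 1.0 = 600. A 50% rise in area hides full recovery of symmetry.

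**Power, illustrative only.** Assumptions: deviation of left % from 50 is normal with SD 5 and mean 0, 2.5 or 5; follow-up deviation in one arm is multiplied by 0.9, 0.75 or 0.5 and the other arm is unchanged; within-patient correlation 0.3, 0.6 or 0.8; 25 per arm; Welch test on change; 8,000 simulated trials per scenario.

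| Mean lean | Fall in imbalance | Signed, corr. 0.6 (range 0.3-0.8) | Absolute, corr. 0.6 (range 0.3-0.8) |
|---|---|---|---|
| None | 10% | 4.8% (4-5%) | 7.1% (7-8%) |
| None | 25% | 5.0% (4-5%) | 17.6% (15-27%) |
| None | 50% | 5.0% (4-5%) | 58.3% (46-77%) |
| Half an SD | 10% | 5.6% (5-6%) | 6.9% (6-9%) |
| Half an SD | 25% | 7.6% (7-11%) | 20.2% (14-31%) |
| Half an SD | 50% | 16.9% (13-27%) | 63.5% (51-84%) |
| One SD | 10% | 6.9% (7-9%) | 8.2% (8-11%) |
| One SD | 25% | 17.0% (12-29%) | 27.6% (18-44%) |
| One SD | 50% | 52.5% (34-76%) | 78.4% (60-95%) |

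Hand check of one cell (one SD, 50% fall, correlation 0.6, signed). The difference in mean change is 0.5 x 5 = 2.5. The variances of change are 25 + 6.25 - 2 x 0.6 x 12.5 = 16.25 and 25 + 25 - 2 x 0.6 x 25 = 20. The standard error is sqrt((16.25 + 20)/25) = 1.204 and the ratio is 2.08, which corresponds to power just above one half, in line with 52.5%.

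**The case against.** **The protocol's wording is ambiguous.** A difference between two percentages can be read as a magnitude. That stands for protocol 9.6.3.2 alone. It does not rescue the SAP, whose endpoints are the two unfolded percentages.

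**SKDI already ignores direction, and sway area is modelled on its own.** An opposite movement in area would therefore be visible. True, but SKDI never isolates symmetry, so it cannot answer the question that this parameter was added for.

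**The averaging step is already gone from the SAP's distribution endpoints.** SAP 6.2.2 keeps eyes open and eyes closed apart. That stands, and folding per record is consistent with it. The order still matters if the protocol's mean is ever reported: averaging 60/40 and 40/60 first gives 0, while folding first gives 20.

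**The power table favours the case by leaving one arm unimproved.** Both arms are treated, and protocol 9.2.1.1.3 says adult symptoms usually resolve in 10 to 14 days. With the comparator's deviation halved and the other arm reduced by a further 10%, 25% or 50%, power for the absolute measure with no mean lean falls to roughly 5-28%, while the signed measure stays near 5%. With a one-SD lean and the largest effect it is 15-22% signed against 25-37% absolute. The table also uses a two-sample test on change, not the planned mixed model. It illustrates and does not estimate. The cancellation and the unreadable sign do not depend on it.

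**Replacing a planned analysis after a data review risks selective reporting.** The risk is real. It is met by an open post hoc label and by keeping left % as a descriptive row.

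**Conclusion.** The concern holds. Carried out as written, the SAP's models for left % and right % let recoveries from opposite sides cancel: fully when leaning is evenly split, partly otherwise. The sign of a mean change reflects the mix of sides, not improvement. The additional all-patient D0 to D52 model (note at the end of SAP 8.5.1.3) also covers balance function and inherits the problem for these variables.

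The reach is limited to one exploratory balance parameter. The primary safety endpoint, the sample size and the sway-area analysis are untouched. The cancellation and the mirror-image models need only the 50/50 reference and percentages that sum to 100. The size of any power gain rests on assumed inputs; it is small for small effects and shrinks if both arms recover. The main gain is a result whose direction can be read.

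**What to change.** - In SAP 6.2.2, derive the absolute value of left % minus right % for each record, eyes open and eyes closed separately and before any averaging. Add a matching note to protocol 9.6.3.2.
- Model this variable under SAP 8.5.1.1, and in the D0 to D52 model, in place of left %, right % and the unfolded difference. State that a fall is an improvement.
- Check residuals, because the variable is bounded at 0, and name a fallback method before the model is run.
- Drop the right % model; keep left % as a descriptive row.
- In SAP section 10, list this change together with the unlisted move from the protocol's difference to two separate percentages. Label the change as made after the data review of 18/07/2023, and carry that label into the report.

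The cost is one derived variable per record, the text edits above and a post hoc label. No new data are needed, and eight duplicate p-values disappear.
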